In Phase II, we will conduct an evaluation of the intervention applying a group-randomized design with village as the unit of assignment. Sixteen villages were selected and randomly assigned to receive the intervention (8 villages) or control condition (8 villages) with ≥ 22 pregnant women recruited per village.

Subject population:

Sample size calculation. We estimate recruiting ≥ 22 pregnant women per village (N=352). Accounting for an estimated attrition rate of 10% due to miscarriage, abortion or fetal demise, we plan to achieve a final sample of at least 320 women eligible for follow-up. All pregnant women (tobacco users and non-users) will be eligible for enrollment.

Actual accrual. We met our targeted sample size of 352 women enrolled. Encouragingly, overall participation from control villages (n=164) was similar to overall participation from intervention villages (n=188). Although we estimated 22 or more women enrolled in each village, this was not feasible. Study villages were more or less interested in participating, with a range of 2 to 42 women enrolled in the 16 study villages.

Inclusion Criteria:

Participants consist of 352 Alaska Native pregnant adults age 18 and older. To be eligible for the study, Alaska Native pregnant women participants must:

- Be 18 years of age or older
- Provide written informed consent
- Currently 36 weeks or less gestation
- Access to a working telephone

Exclusion Criteria:

Individuals will be considered ineligible to participate in the study if they are:

- Not Alaska Native
- Under the age of 18
- Currently not pregnant or ≥ 37 weeks gestation
- No access to a working telephone
- Refuse to provide written informed consent

Will a Certificate of Confidentiality be obtained? If yes, provide an explanation.

No, a Certificate of Confidentiality will not be obtained.

Study Design

Methods: *Describe, in detail, the research activities that will be conducted under this protocol:*

Phase IA. Social Marketing Campaign Development

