For intervention villages, we will assess the pregnant woman's reported exposure to the social marketing campaign using continuous scales adapted from prior research. For example, her awareness/recall of the campaign messages and media (e.g., point of purchase displays), if she used/read various campaign media such as brochures and viewed the digital stories DVD, and if she shared these materials and/or the information with others in her village. An intervention exposure index will be created based on item responses to permit exploration of dose response effects.

De-identified data will be obtained from the YKDRH on the total number of positive pregnancy tests in each randomized village during the recruitment period. The study staff will track recruitment data, completion of each follow-up assessment among enrolled participants and use of NRT/other treatments.

To inform dissemination efforts, we will track and summarize the cost of intervention components including time spent by the Native Sisters and program materials displayed/distributed in each village. We will exclude development costs, as these would not be considered in disseminating the intervention.

Dissemination Plan To communicate and introduce the study to the local community we submitted a story to the region-specific "Tundra Drums" newspaper and locally owned radio stations (KYKD, KYUK). Dissemination of the results will occur after each phase of the project with guidance from our CAC. The first level of dissemination will be to the YKHC Human Studies Committee and Board. After receiving approvals, the second level of dissemination will be to the local community by submitting a story to local newspapers, locally owned radio stations, and the YKHC employee website. A booklet or brochure and a power point presentation with key project findings will be developed and approved by the YKHC. Presentations will be given to community members at local gatherings in Bethel and to YKDRH providers. The YKHC staff will also travel to the study villages to provide promotional items from the campaign, along with the brochures and DVD digital stories. They will meet with village councils to share results as feasible.

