who quit tobacco use during pregnancy, the relapse rate was 63% at 6 weeks postpartum. Of the 432 women reporting no tobacco use in the three months before pregnancy, 75% reported tobacco use during the prenatal period, and 70% at 6 weeks postpartum. Alaska PRAMS data indicate similar cessation rates during pregnancy (20%) and rates of relapse postpartum (57%) in the southwest region. During the time periods these estimates were obtained, women received the same standard of care as in the proposed study. Therefore, we do not expect our usual care condition to impact tobacco use beyond the natural history of tobacco use in pregnancy. The Clinical Practice Guideline meta-analysis found that behavioral/psychosocial interventions for pregnant smokers were associated with an abstinence rate of 13% in late pregnancy vs. 7% for control conditions (OR= 1.8, 95% CI 1.5-2.3). We do not have guidance from the literature on the possible impact of interventions for baseline non-tobacco users but would expect greater impact in this group compared to those already using tobacco. Accordingly, we estimate the rate of tobacco use at 6 months postpartum to be 70% in our control villages and 55% in the intervention villages (estimated odds ratio 1.91) and in late pregnancy to be 80% vs. 65% with an odds ratio of 2.15. A difference of 15% would be of clinical significance in terms of the potential to impact the current standard of care at the YKDRH.

Estimates of intra-class correlations (ICC) within communities are quite modest, e.g., ranging from 0.002 to 0.012 for a variety of survey variables included in the Minnesota Heart Health Program. For the proportion currently smoking the estimated ICC was 0.00272. Other literature indicates that in community based trials using group-randomized designs (e.g., NCI Working Well Trial) the ICC ranged from 0.01-0.03 for the four outcome variables at baseline. Lumley et al. reviewed 9 cluster randomized trials of prenatal cessation interventions but most did not report the ICC and/or account for the clustering effect in the analysis. Table 3 (below) provides power estimates for the estimated outcomes with 16 villages total, average village participant size of 20 (total sample size = 320), and with varying ICC estimates. With an ICC of 0.01 we will have >80% power to detect the hypothesized differences between conditions at 6 months postpartum.

Table 3. Power estimates for 1-sided alpha=0.05 test

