We will follow procedures suggested by MacKinnon to assess mediation (**Aim 2**), fitting three GEE models to the data. We will first estimate the intervention effect separately for the dependent variable (with regression adjustment for covariates). That model provides an estimate of the total effect of the intervention, which MacKinnon labels C. Next we will estimate the intervention effect for each mediator (with regression adjustment for covariates); that model provides an estimate of the effect of the intervention on the mediator, which MacKinnon labels A. Finally we will estimate the mediated intervention effect for the dependent variable by adjusting for the mediator (and covariates); that model provides an estimate of the unmediated (i.e., direct) intervention effect, which MacKinnon labels C, and the intervention-adjusted effect of the mediator on the dependent variable, which MacKinnon labels B. Assuming an ICC of 0.01 and an effective sample size of 270 subjects after correction for the ICC, there will be 80% power to detect an effect size of at least 0.35 standard deviation units for paths A and B assuming a two-sided, alpha=0.05 test at 6-months postpartum.

Treatment condition differences on changes in other variables targeted (see Table 4) will be examined using GEE with a logit (binomial outcome) or identify (continuous outcome) links as appropriate.

We will summarize the cost of the program per pregnant woman enrolled (reached) along with cost per woman abstinent from tobacco at 6 months postpartum follow-up using descriptive statistics.

Endpoints

Primary:

Biochemically confirmed tobacco abstinence at 6-months post-partum.

Secondary:

Biochemically confirmed tobacco abstinence at end of pregnancy. Also, changes in proposed theory-based mediators of intervention efficacy.

Project Timeline

We have received approval from NIH to extend out the study timeline from 5 to 6 years total. We are currently beginning the 5th year of our 6-year NIH grant. Table 4 shows the timeline for the remaining Phase II

activities. We will request from NIH a 7th project year as a no-cost extension to complete analyses and dissemination if necessary and long as remaining funds permit.

Table 4

PROJECT TIMELINE, YEARS 3-7,
Dates: May 1, 2015 – April 30, 2020

Activity	Year 3 2015-2016				Year 4 2016-2017				Year 5 2017-2018				Year 6 2018-2019				Year 7 2019-2020 No Cost Extension					

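### The plan gives an average cost per abstinent woman but no cost per additional abstinent woman, although the trial has a usual-care arm and the cost result is meant to guide dissemination

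*Combined protocol and SAP*

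**What the plan says.** The cost analysis is described in two places.

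- **Program Evaluation** gives the purpose and the numerator: "To inform dissemination efforts, we will track and summarize the cost of intervention components", covering interventionist time and programme materials in each village. Development costs are left out: "We will exclude development costs, as these would not be considered in disseminating the intervention".
- **Statistical Considerations, Phase II, Data Analysis Plan** gives the measures. One is programme cost per pregnant woman enrolled. The other is "cost per woman abstinent from tobacco at 6 months postpartum follow-up using descriptive statistics". The text does not say which arm's abstinent women are counted, does not subtract control-arm abstinence, and gives no interval.

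Three other statements bear on how the second measure will read.

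- The **Power Statement** sets 6-month tobacco use at "70% in our control villages and 55% in the intervention villages", which is 30% and 45% abstinence.
- The same section says of the control condition that "we do not expect our usual care condition to impact tobacco use beyond the natural history of tobacco use in pregnancy". The 30% is therefore what the plan expects without the programme.
- The Phase II **Subject population** section says "All pregnant women (tobacco users and non-users) will be eligible for enrollment". Baseline non-users who are still non-users at 6 months count as abstinent.

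**The concern.** A health system deciding whether to adopt the programme needs to know what each abstinent woman gained would cost. Dividing programme cost by all abstinent women in intervention villages answers a different question, because many of those women would be abstinent anyway. At the plan's own rates they are the majority.

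The average also says little about whether the programme works. It stays finite when there is no effect, and it changes only modestly as the effect shrinks, while the cost of each additional abstinent woman rises without limit. A reader who takes the average as the price of a gained abstainer would be misled most when the effect is smallest. The trial has a randomised usual-care arm, so the more useful figure can be derived from data already being collected.

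**Working it through.** **Inputs**

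- Hypothesised abstinence at 6 months (Power Statement): p_I = 1 − 0.55 = 0.45 and p_C = 1 − 0.70 = 0.30.
- Planned analysis sample (Power Statement): 320 women in 16 villages, average 20 per village, so 160 per arm.
- Planned enrolment (Subject population): 352, so 176 per arm.
- The documents give no cost figure. Write C for total programme cost in intervention villages, n for intervention women eligible for follow-up, and k = C/n.

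**Step 1. Reproduce the plan's own figure from the same rates.** The design effect at ICC 0.01 is 1 + 19 × 0.01 = 1.19, so the effective size is 160/1.19 = 134.5 per arm. A one-sided 0.05 test of 55% versus 70% then has power 81.8%. Table 3 states 81%. The stated odds ratio also reproduces: (0.70/0.30)/(0.55/0.45) = 1.91. The rates are therefore being read as the plan uses them.

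**Step 2. The two cost measures.**

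- Average cost per abstinent woman = C/(n × p_I)
- Cost per additional abstinent woman = C/(n × (p_I − p_C))
- Ratio of the second to the first = p_I/(p_I − p_C)

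Usual care is given in both arms (Figure 1), so programme cost is already a reasonable incremental numerator. Only the denominator differs.

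**Step 3. At the plan's rates.** With n = 160, 160 × 0.45 = 72 women are abstinent, 160 × 0.30 = 48 would be expected under usual care, and 72 − 48 = 24 are additional. The planned figure is C/72 = 2.22k. The incremental figure is C/24 = 6.67k. The ratio is 0.45/0.15 = 3.0. It does not depend on C or n, nor on loss to follow-up counted as tobacco use if that loss is equal in the two arms.

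**Step 4. Other effects, with control abstinence held at 30% (assumed range).**

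| Gain | Average | Per additional abstainer | Ratio |
|---|---|---|---|
| 20 points | 2.00k | 5.00k | 2.5 |
| 15 points (plan) | 2.22k | 6.67k | 3.0 |
| 10 points | 2.50k | 10.0k | 4.0 |
| 5 points | 2.86k | 20.0k | 7.0 |
| none | 3.33k | not defined | – |

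With the gain held at 15 points and control abstinence assumed between 20% and 35%, the ratio runs from 0.35/0.15 = 2.3 to 0.50/0.15 = 3.3.

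**Step 5. Which women go in the denominator.** The outcome analysis excludes women with pregnancy loss, but the plan's first cost measure is per woman enrolled. If K is cost per enrolled woman, then at the planned 352 enrolled and 320 eligible, k = K × 352/320 = 1.1K. The cost per additional abstainer is K/(0.15 × 320/352) = 7.3K. Dividing K by 0.15 would give 6.7K, about 9% too low. The average is likewise 2.4K rather than 2.2K. The 3.0 ratio is unchanged.

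**Step 6. Precision.** At 45% versus 30% and 134.5 effective women per arm, the standard error of the difference is √((0.45 × 0.55 + 0.30 × 0.70)/134.5) = 0.058.

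- At a 15-point difference, a t interval on 14 df is about 2.5 to 27.5 points, which inverts to about 3.6k to 40k.
- At a 5-point difference, the normal interval is about −6 to +16 points. It includes zero, and inverting its ends does not give a valid range.

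**The case against.** The plan does not claim what a critical reader might fault it for. It promises a descriptive summary. It does not call the ratio incremental, attributable to the programme, or a measure of cost-effectiveness. An average cost that is correctly described does not understate some other quantity. This stands: what is missing is a comparator, and the risk is misreading.

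The denominator is inferred. Only intervention villages carry programme cost, so their abstinent women are the natural count, but the text does not say so. If abstinent women in both arms were counted, the gap at 160 per arm would be (72 + 48)/24 = 5-fold.

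The ingredients are already planned. Tobacco use will be reported by condition with 95% confidence intervals, and a null efficacy result would be visible alongside the cost. A reader could form a crude incremental ratio, and nothing is lost in design or data collection. That limits the importance of the point but does not remove it. A crude ratio formed from cost per enrolled woman would mix populations (step 5) and carry no interval.

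A reader might also infer that the plan understates the cost of success three-fold as a matter of fact. The documents do not support that. Three-fold holds only at the hypothesised rates. Nor do they support calling the average figure attractive, since they give no cost and no threshold.

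**Conclusion.** The point holds as a low-priority, cheap improvement. The plan has an average cost per abstinent woman and no cost per additional abstinent woman, although the cost result is meant to inform dissemination and a usual-care arm is available. At the hypothesised 45% versus 30% abstinence the average is one third of the incremental figure. The gap is 7-fold at a 5-point gain, and the average remains 3.33k per abstinent woman if there is no effect.

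These sizes assume that the denominator is abstinent women in intervention villages, that loss to follow-up is similar in the two arms, and that the rates are those in the Power Statement or in the ranges shown. The point does not affect the primary endpoint, the sample size or the efficacy analysis.

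**What to change.** Add one measure to the Data Analysis Plan: cost per additional abstinent woman = total programme cost in intervention villages ÷ (intervention women eligible for follow-up × difference in confirmed abstinence at 6 months).

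- **Difference.** The planned GEE has a logit link and does not give a risk difference directly. Obtain the difference by standardising the planned village-size-adjusted model, and base its 95% interval on the small-sample correction already specified.
- **Interval including zero.** Report programme cost and the difference with its interval side by side, and state that the ratio has no finite upper limit. Do not invert the interval.
- **Existing measures.** Keep cost per woman reached. State which arm's women form the denominator of the planned ratio, and label it as an average cost not attributable to the intervention.

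This needs no new data. It costs a little more analysis than a descriptive line. The drawbacks are a wide interval (step 6) and a less favourable figure.
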